## 15.8 Overall survival (OS)

Overall survival (OS) is defined as the time (months) from the date of the first IMP administration to the date of death due to any cause.

If a subject is not known to have died, then OS will be censored, and the censoring date will be the latest date the subject was known to be alive (on or before the cut-off date).

OS will be analyzed in the FAS population and presented graphically as well as summarized using survival analysis methods:

- Kaplan-Meier curves
- Kaplan-Meier estimates of the median time, the first and third quartiles, along with approximate 95% confidence interval of the median (the default conftype=loglog in SAS PROC LIFETEST will be used).

#### 16. Pharmacokinetic Evaluation

The pharmacokinetic evaluation described below is part of the secondary objective.

The calculation of the pharmacokinetic endpoints will be performed by

Individual curves of plasma/serum concentration of each component of GEN1029 (Hx-DR5-01 and Hx-DR5-05), including information on actual dose, will be presented for all subjects in the PK set. All available data will be shown in these figures. Additional graphs of PK concentration will present the ADA values and the values of the titers.

The results will also be summarized descriptively over time according to the planned PK sampling schedule.

Mean graphs for the plasma/serum concentrations by cycle (for cycle 1, cycle 2 and cycle 3) and dose level will be presented both with and without error bars. The value <BLLoQ will be replaced by the numerical LLoQ value divided by 2 and mentioned in a footnote.

Approved in Vault: 07 Mar 2022

TPL N°: eTPL SA-02-01 TPL Version: 02 Of SOP SA-02.08

TPL Effective Date: 31 Mar 2016

In addition, descriptive statistics for each clone will be calculated and presented for all non-compartmental PK parameters (e.g.  $C_{max}$ ,  $T_{max}$ ) for Cycle 1, Cycle 2 and Cycle 3. This will include mean (arithmetic and/or geometric), median, min, max, n, standard deviation (SD), and geometric coefficient of variation (CV%) of the PK parameters of GEN1029.

Geometric CV% will be calculated as follow:

Geometric CV% = (sqrt(exp(variance for log transformed data)-1))\*100

Geometric mean and CV% will not be calculated for Tmaxand T1/2.

Missing concentration values will be reported as it is in data listings. Concentration values below lower limit of quantitation (BLLOQ) will be handled as lower limit of quantitation (LLOQ)/2 in summary statistics and reported as it is in data listings. Any missing PK parameter data will not be imputed.

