		mg IV), could be part of the premedication regimen as per protocol.
Amendment 4, v6.0	07-Feb-2019	 Initial PK data suggested that PK appears to be very similar for the 2 antibodies (1029-01 and 1029-05). However, human PK predictions based on the nonclinical model appear to have significantly underestimated the observed human clearance of both 1029-01 and 1029-05. Predictions for Cmax have been very accurate and increase of Cmax appeared to be dose-proportional. However, since the clearance in humans appeared to be significantly higher than predicted, Ctrough values for both GEN1029 component antibodies were below the lower level of quantification (based on 14 days dosing interval) and AUC0-14days was also below the predicted values. Thus, based on limited PK data from 10 subjects at doses of 0.3-3 mg/kg in dose escalation cohorts, plasma half-life (T1/2) appeared to be relatively short, ranging from 15 to 63 hours. To achieve higher exposures in subjects and potentially provide opportunity to achieve the best therapeutic response, 2 additional dose regimens were introduced with this amendment: An Intensified Regimen: subjects dosed once weekly for the first 8 weeks then once every 14 days thereafter (8×Q1W/Q2W) to obtain higher drug exposures and thereby potentially improve the anti-tumor efficacy. A Priming Regimen: in the first cycle, subjects received 2 weekly priming doses. Thereafter, they were dosed once every 14 days (Priming/Q2W) to potentially enable tolerance of increased dose levels and consecutively providing higher exposures. The concept of a priming dose has been successfully implemented for multiple drugs to desensitize the system to prevent eg, tumor lysis syndrome, cytokine release and infusion reactions. This may potentially lead to tolerance of higher dose levels as well as increasing the therapeutic window.
		The total maximum planned number of subjects was increased from 188 to 549, partly because of the additional dose regimens and partly because of the introduction of a Bayesian predictive probability approach for the Expansion.
Amendment 3, v5.0	15-Mar-2018	The original protocol version 2.0 dated 04 October 2017 was submitted to the FDA and MHRA. In order to address the recommendations and requests from the FDA, amendment 1, dated 06-Dec-2017, was prepared. Similarly, amendment 2, dated 13-Dec-2017, was prepared to address the comments and requests from MHRA.

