3 OBJECTIVES AND ENDPOINTS

Objectives and related endpoints are described in Table 3-1.

Table 3-1 Objectives and Endpoints

Dose Escalation Part

Objectives			Endpoints		
Pri	mary				
•	Determine the MTD and/or the recommended Phase 2 dose (RP2D) Establish the safety profile of GEN1029	•	Dose limiting Toxicities (DLTs) Adverse events (AEs) and safety laboratory parameters (hematology and biochemistry)		
Sec	condary				
•	Establish the PK profile and evaluate immunogenicity of GEN1029 after single and multiple infusions	•	PK parameters (clearance, volume of distribution and area-under-the-concentration-time curve $[AUC_{0-Clast}$ and $AUC_{0-\infty}]$, $AUC0_14d$, CL. maximum concentration $[C_{max}]$, time of C_{max} $[T_{max}]$, pre-dose values, and half-life of GEN1029		
		•	Immunogenicity of GEN1029		
•	Evaluate the anti-tumor activity of GEN1029	•	Anti-tumor activity measured by tumor shrinkage (based on computerized tomography [CT]-scan evaluations)		
		•	Objective Response, Progression-Free Survival (PFS), Overall Survival (OS), Duration of Response (DoR), and Time to Response (TTR)		
Ex	ploratory				
•	To assess biomarkers predictive of response or resistance to GEN1029	•	DR5 expression (protein,) in tumor biopsies		
•	To assess potential pharmacodynamic biomarkers of	•	Circulating protein profiles		
	GEN1029	•	Immune cells levels		
		•	Biomarker profile		
•	To assess the metabolic response in the tumors	•	Standardized uptake volume corrected for body lean mass (SUL)		
•		•			

Expansion Part

	Objectives	Endpoints			
Pri	mary				
•	To evaluate the Objective Response Rate (ORR) by indication	• ORR			
Sec	condary				
	Evaluate the anti-tumor activity of GEN1029	• Anti-tumor activity measured by tumor shrinka (based on computerized tomography [CT]-so evaluations)	age can		
		• Objective Response, Progression-Free Survival (PF Overall Survival (OS), Duration of Response (Do and Time to Response (TTR)	'S), R),		
•	To further describe the safety profile of GEN1029	• Adverse events (AEs) and safety laboratory paramet (hematology and biochemistry)	ters		
	Evaluate the pharmacelyinetic (D K) profile as feasible	DV noremeters			
•	Evaluate immunogenicity of GEN1029 after single	• FK parameters			
and multiple infusions		Immunogenicity of GEN1029			
Ex	ploratory				
•	To assess biomarkers predictive of response or resistance to GEN1029	• DR5 expression (protein, DR5) in tun biopsies	nor		

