#### 3.2 Trial Design

The trial design details are available in section 4 Trial Design of the protocol final version 9.0 dated 24 October 2019.

Unless other events, subjects are intended to receive GEN1029 until PD. Note that the treatment may be stopped due to other reasons.

In the dose escalation part, up to 3 dose regimens were evaluated:

- The Biweekly Regimen: subjects are dosed once every 14 days (Q2W)
- The Priming Regimen: in the first cycle, subjects receive a priming dose; after 14 days and thereafter, they are dosed with the full dose once every 14 days (Priming/Q2W).
- The Intensified Regimen (protocol v8.0): 8xQ1W/Q2W: subjects are dosed every week for the first 8 weeks and then they are dosed once every 14 days.

F

Page 7 of 44

TPL N°: eTPL SA-02-01 TPL Version: 02 Of SOP SA-02.08

For the assessments of each cohort the dose limiting toxicities (DLT) will be collected for the first two cycles i.e. DLT period of 28 days.

The dose escalation part will be performed as a modified Bayesian Optimal Interval (mBOIN) design.

More details can be found in section 4.3 of the protocol final version 9.0 dated 24 October 2019.

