## 4.5 Treatment Assignment and Treatment Arms

Data will be grouped according to treatment dose level in the biweekly regimen, as described below, rather than by 'treatment arm'. Intensified and Priming regimen only have 1 subject per regimen and will be provided only in listings (cf. section 3.3).

In biweekly regimen, subjects will receive one infusion of GEN1029 every second week. The following doses are planned: 0.1 mg/kg, 0.2 mg/kg, 0.3 mg/kg, 1.0 mg/kg, 2.0 mg/kg and 3.0 mg/kg. Other dose levels were planned in the protocol v9.0, as the MTD was identified, those were not investigated.

Results will be grouped according to dose-level and total.

All data will be listed by dose level, subject ID (subject treatment number), site ID and visit (if applicable). Data related to screen failures will be listed by screening number.

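### Replacing unquantifiable concentrations by LLOQ/2 makes trough summaries uninformative wherever most or all values are below the limit, and no table shows how many are

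*SAP*

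**What the plan says.** Table 3-1 of the protocol includes "pre-dose values, and half-life of GEN1029" among the secondary PK endpoints of the dose escalation part. Protocol Table 1-3 schedules PK samples at screening and before infusion on Day 1 of each cycle. Protocol section 11.4.4 plans to explore pre-dose values against anti-drug antibody (ADA) status.

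The sponsor already had evidence on troughs. The Amendment 4 entry in the protocol's summary of amendments reports that "Ctrough values for both GEN1029 component antibodies were below the lower level of quantification (based on 14 days dosing interval", and that half-life "appeared to be relatively short, ranging from 15 to 63 hours". The half-life finding is described as "based on limited PK data from 10 subjects at doses of 0.3-3 mg/kg in dose escalation cohorts". I use this as reported data, not as superseded plan text.

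For the analysis, SAP section 16 states: "The results will also be summarized descriptively over time according to the planned PK sampling schedule". Values below the limit are then treated as follows: "Concentration values below lower limit of quantitation (BLLOQ) will be handled as lower limit of quantitation (LLOQ)/2 in summary statistics". SAP section 4.8 repeats this rule. SAP section 16 applies it to the mean graphs, with a footnote, and protocol section 11.4.3 applies it to the individual curves. Data listings keep the values as reported. The standard continuous summary in SAP section 4 is n of non-missing values, mean, SD, median, quartiles, minimum and maximum. Neither document plans a count of values below LLOQ, a condition for withholding a mean, or a separate rule for samples taken before the first dose.

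**The concern.** Single-value substitution is a tolerable convenience when few values are below the limit. Here the protocol's own data suggest that, for a named endpoint, most or all of them may be. The summary then describes the substitution rule and not the drug. A trough row would show a non-zero concentration with no spread, the same at every dose, and equal to the value shown before any drug was given. The result a reader needs is how many subjects had a measurable trough at each dose, and no planned table gives it. Where all troughs are below LLOQ, comparing pre-dose values by ADA status compares a constant with itself.

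**Working it through.** **Inputs**
- Dosing interval: "The Biweekly Regimen: subjects are dosed once every 14 days (Q2W"), that is 14 × 24 = 336 h (SAP 3.2).
- Half-life: 15 to 63 h (protocol, Amendment 4 entry).
- Dose levels: "The following doses are planned: 0.1 mg/kg, 0.2 mg/kg, 0.3 mg/kg, 1.0 mg/kg, 2.0 mg/kg and 3.0 mg/kg" (SAP 4.5).
- LLOQ: not in the documents. Call it L, one constant for each component's assay.

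**1. Are unquantifiable troughs plausible?** With mono-exponential decline, the fraction of peak left at trough is 0.5^(336/half-life).
- 15 h: 336/15 = 22.4 half-lives; 0.5^22.4 = 1.8 × 10⁻⁷, about 0.00002% of peak.
- 63 h: 336/63 = 5.33 half-lives; 0.5^5.33 = 0.0248, about 2.5% of peak.
- Accumulation is 1/(1 − fraction), at most 1/(1 − 0.0248) = 1.03, so later cycles barely raise the trough.

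This agrees with the sponsor's report. The 0.1 and 0.2 mg/kg levels lie below the doses on which that report rests.

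**2. All values below LLOQ.** Each becomes L/2. Then mean = median = minimum = maximum = L/2 and SD = 0 at every dose from 0.1 to 3.0 mg/kg. If exposure were dose-proportional with the same half-life, true troughs would differ 3/0.3 = 10-fold between 0.3 and 3 mg/kg, and 3/0.1 = 30-fold between 0.1 and 3 mg/kg. The reported ratio would be 1. The n column does not help, because substituted values count as non-missing.

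**3. Most values below LLOQ.** Illustration with six subjects, five below LLOQ and one at 2L: mean = (5 × 0.5L + 2L)/6 = 4.5L/6 = 0.75L; median = 0.5L. The mean and SD are no longer constants, but the median is still the substituted value. This holds whenever more than half are below LLOQ.

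**4. Before any drug.** Screening and Cycle 1 pre-first-dose samples contain no GEN1029. If they read below LLOQ, as expected, they are also shown as L/2, the same number as an unquantifiable trough.

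**5. Size.** A value below LLOQ lies between 0 and L, so each substitution is wrong by at most L/2. Without L this cannot be put in concentration units.

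**The case against.** The strongest reply is that troughs need not be unquantifiable throughout. The evidence is early and comes from 10 subjects, while SAP section 3.3 expects 48. The half-life range leaves room too. Assume, since the documents give neither figure, a distribution volume of 0.045 L/kg and half the dose per antibody. At 63 h the 14-day level is then (dose/2)/0.045 × 0.0248, or 0.28, 0.55 and 0.83 µg/mL at 1, 2 and 3 mg/kg. At 3 mg/kg, volumes of 0.04 to 0.06 L/kg give 0.93 to 0.62 µg/mL. An assay with an LLOQ of 0.1 µg/mL (also assumed) would measure all of these, in dose order. This stands: a reader might infer that troughs will come out as one dose-independent constant, but that follows only where all values at a dose level are below LLOQ.

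Three other stronger readings also fail:
- **A flat stretch from Day 8 to Day 15 in the mean curves.** The mean graphs are drawn by cycle, time zero is each cycle's Day 1 infusion (SAP 4.6), and Day 8 is the last scheduled sample within a cycle. The reported finding concerns the 14-day trough, not Day 8.
- **A stated fold error.** Any such figure rests on an LLOQ and a volume that the documents do not give.
- **Harm to the choice of RP2D.** SAP section 5 does call PK essential for that choice, but in order to justify defining a PK analysis set. By this SAP version the MTD had been found and the expansion part was not initiated. The non-compartmental parameters in protocol Table 11-1 do not include trough, and the SAP does not say whether substituted values enter their calculation.

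It is also fair that the rule is prespecified, consistent between protocol and SAP, and disclosed in the listings and graph footnote. A row with minimum equal to maximum and SD 0 would look imputed to an alert reader. That helps only when all values are below LLOQ. In the mixed case, the table gives no sign of how much of the mean was measured.

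**Conclusion.** The point stands as a reporting weakness in a secondary PK endpoint. At any dose level and time point where all values are below LLOQ, the planned summary is LLOQ/2 with SD 0 regardless of dose. Where more than half are below it, the median is LLOQ/2. Unquantifiable samples taken before the first dose receive the same value. No summary table shows the share affected. The arithmetic needs no assumption about LLOQ or volume. How often it applies depends on whether later troughs resemble those in the first 10 subjects, and the documents cannot settle that. The constant may differ between the two antibodies, because each has its own assay. The documents do not support extending the point to AUC, Cmax, half-life, MTD or RP2D, and the error cannot be sized beyond the bound of LLOQ/2 per value.

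**What to change.** Amend SAP sections 4.8 and 16 as follows:
1. At each time point, by dose level and component, report the number and percentage of values below LLOQ.
2. Where more than half are below it (or another share fixed in advance), print the median as '<LLOQ', give no mean or SD, and plot no mean at that point.
3. Set pre-first-dose values below LLOQ to zero.
4. Summarise pre-dose values, including by ADA status, as the proportion quantifiable.

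The one-half threshold is a convention. What matters is that some threshold is fixed beforehand. Because protocol section 11.4.3 carries the LLOQ/2 rule, record the change in SAP section 5. The cost is SAP wording and a programming rule, with no new data. The downside is that some time points will have no mean.

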## 17. Safety Evaluation

All safety results will be presented on the safety set (SAF).

## 17.1 Primary Endpoint: Dose-limiting Toxicities (DLT)

DLT definition is provided in protocol V9.0 section 7.1.

All analyses on the primary endpoint will be done on the dose-determining set in the dose escalation part of the trial.

The number of subjects with a DLT will be presented for each dose-level. All the DLT information will be included in a graph marking subjects who have no DLT and have a DLT in order of inclusion, also indicating the subjects which are not evaluable for DLT (not part of the DDS).

Subjects excluded from the DDS and the reasons will be listed.

#### 17.2 Extent of Exposure

The actual cumulative dose, actual and relative dose intensities (continuous and in categories: >= 110%, 90% to < 110%, 70% to < 90%, 50% to < 70%, < 50%, missing), the number of subjects with a dose reduction and the reason of dose reduction (AE/Other) of GEN1029 will be listed and summarized by means of descriptive statistics together with the duration in days. Also, the number of subject days (total number of days in trial) and the number of days on treatment will be presented by means of descriptive statistics for each dose group. The duration of GEN1029 in days by ADA status will also be presented.

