## 3.3 Sample Size Justification

The protocol v9.0 planned to enroll up to approximately 100 subjects shared between the Regimens. As the MTD was found earlier than the highest dose level planned in the protocol and the expansion will not be initiated, only 48 subjects will be recruited.

Of those 48 subjects:

Page 8 of 44

TPL N°: eTPL SA-02-01 Of SOP SA-02.08 TPL Effective Date: 31 Mar 2016

- Two subjects were assigned to the priming regimen:
- One received the priming dose and then continued on a lower dose level. This subject is considered as treated on the 'biweekly regimen'.
- The second subject received the priming dose and continued with a higher dose level, this subject will be analysed as treated in the priming regimen.
- Three subjects were also planned in an Intensified Regimen (8xQ1W/Q2W) all of whom experienced DLTs and, consequently, this dosing regimen was permanently discontinued.

The Intensified Regimen was discontinued per protocol v9.0.

More details on sample size can be found in section 11.8 Sample Size Calculation of the protocol final version 9.0 dated 24 October 2019.

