## 4.4 Subgroup Definitions

If at least 5 subjects per subgroup per dose level are available, subgroup analyses by ADA-positivity are planned.

Other sub-group analyses may be performed post-hoc. Due to the low expected number of subjects per site no investigation of site effects is planned.

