## 15.4 Objective response rate (ORR)

The objective response rate is the proportion of subjects with either CR or PR as best overall response. This is presented as part of the BOR summaries.

Similarly, the ORR including both confirmed and unconfirmed responses will be presented as a supportive analysis.

In addition, ORR will be analyzed by subgroup (as described in section 4.4) using a forest plot.

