## 18. Other Safety Data

## 18.1 Immunogenicity (anti-drug antibodies) of GEN1029

Data on immunogenicity (anti-drug antibodies) of GEN1029 will be summarized as described below on the immunogenicity set.

Titers of GEN1029 will be listed additionally to their presentation in graphs of PK concentration and pharmacokinetic table

[figure not shown]
Positive/negative host immune response to GEN1029 will be tabulated by visit. For post-baseline results, a subject will have a positive ADA status if negative at baseline and at least one positive post-baseline result, or positive at baseline and at least one positive post-baseline result with a titer higher than baseline. Of note, subjects with no post-baseline ADA assessment will have a missing ADA status.

Of note, ADA positivity requires confirmation in 2 assay steps. First step has many false positive; the second assay step (confirmation) ensures specificity of the assay. Only confirmed ADA positivity results will be considered as positive.

Page 29 of 44

TPL N°: eTPL SA-02-01 Of SOP SA-02.08 TPL Effective Date: 31 Mar 2016

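### Duration and response are shown by an open-ended ever-positive ADA status, so longer-treated patients have more chance to count as positive; add a Cycle 3 Day 1 landmark display and a footnote

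*SAP*

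**What the plan says.** SAP 18.1 sets the status: "For post-baseline results, a subject will have a positive ADA status if negative at baseline and at least one positive post-baseline result". A subject positive at baseline needs a later titre above baseline. No time limit applies. SAP 18.1 adds that "subjects with no post-baseline ADA assessment will have a missing ADA status", so such subjects are not counted as negative.

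Two displays use this status against outcomes that depend on time:

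- SAP 17.2, without condition: "The duration of GEN1029 in days by ADA status will also be presented".
- SAP 15.4: "In addition, ORR will be analyzed by subgroup (as described in section 4.4) using a forest plot". SAP 4.4 supplies the condition: "If at least 5 subjects per subgroup per dose level are available, subgroup analyses by ADA-positivity are planned".

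Neither section gives a landmark, a time-dependent method or a caveat.

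Protocol Table 1-1 schedules ADA samples at screening, on Day 1 of every cycle, at end of treatment, and 30 and 70 days after the last dose. Protocol 8.3 requires the two follow-up visits whatever the reason for stopping. Protocol 8.2, however, withdraws an escalation patient from the trial, follow-up included, once another anti-cancer treatment starts. Footnote 21 to Table 1-1 then brings the safety visit forward to the time of withdrawal.

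**The concern.** The grouping variable is partly a consequence of the outcome. Each further cycle adds an ADA sample and two more weeks in which antibodies can appear, and one qualifying result labels the subject for the whole trial. A table of duration by that label compares groups that were sorted in part by duration. This is immortal-time bias.

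ORR has the same structure. The first scheduled on-treatment CT falls at Cycle 3 Day 8-14, about Day 36-42, and SAP 15.3 requires at least four weeks before a confirming scan. A confirmed response therefore takes about 10 weeks, by which time a patient still on treatment has had several ADA samples.

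At stake is how immunogenicity is read. Protocol 11.4.4 plans to explore ADA against PK, safety and efficacy, and a reader may take a longer duration in ADA-positive patients as reassurance when it could arise from the classification alone.

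**Working it through.** The documents give no expected difference, ADA incidence, onset time or follow-up attendance, so there is no planned figure to reproduce. The check asks what the displays would show if ADA had no effect.

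**By hand.** Suppose each post-baseline sample is positive with probability p = 10% (assumed). A patient with c cycles has c − 1 pre-dose samples plus one at end of treatment, so c samples, or c + 2 with both follow-up visits. P(ever positive) = 1 − (1 − p)^k, where k is the number of samples.

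| Cycles | No follow-up samples | Both follow-up samples |
|---|---|---|
| 1 | 1 − 0.9^1 = 10% | 1 − 0.9^3 = 27% |
| 10 | 1 − 0.9^10 = 65% | 1 − 0.9^12 = 72% |

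Follow-up sampling narrows the gap but does not close it, because long-treated patients have those visits too.

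**Per-sample model.** Exponential time on treatment, 14-day cycles, 400,000 simulated subjects per setting. Median 4 cycles and p = 10% give these mean durations, ADA-positive against ADA-negative:

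- no follow-up samples: 131 vs 58 days, ratio 2.3 (1.9 to 3.4 over medians of 3-6 cycles and p of 5-20%);
- half attend: 122 vs 58, ratio 2.1 (1.8 to 3.2);
- all attend: 116 vs 58, ratio 2.0 (1.7 to 3.0).

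This model lets every patient turn positive eventually, which favours large ratios.

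**Onset model.** Only a share of patients can form ADA, and onset time is independent of duration and response. Assumed: non-responder median 6 weeks on treatment, true ORR 10%, responders treated at least 12 weeks.

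| Median onset | Share able | Follow-up attended | Mean days, ADA+ vs ADA− | Ratio | ORR, ADA+ vs ADA− |
|---|---|---|---|---|---|
| 4 weeks | 50% | none | 119 vs 79 | 1.5 | 14% vs 8% |
| 4 weeks | 50% | half | 107 vs 83 | 1.3 | 12% vs 9% |
| 4 weeks | 50% | all | 98 vs 89 | 1.1 | 11% vs 9% |
| 2 weeks | 50% | all | 94 vs 93 | 1.0 | 10% vs 10% |
| 8 weeks | 50% | all | 109 vs 84 | 1.3 | 13% vs 8% |
| 4 weeks | 90% | all | 98 vs 69 | 1.4 | 11% vs 6% |
| 4 weeks | 100% | all | 98 vs 32 | 3.1 | 11% vs 1% |
| 4 weeks | 100% | none | 119 vs 32 | 3.7 | 14% vs 1% |

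In one trial of 44 patients with 50% able to form ADA, the chance that the ADA-positive group has the longer mean duration is 73-92% with no follow-up samples, 62-84% with half and 51-73% with all (median onset 2 to 8 weeks). Without bias it would be near 50%.

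**Size condition in SAP 4.4.** There are six dose levels ("0.1 mg/kg, 0.2 mg/kg, 0.3 mg/kg, 1.0 mg/kg, 2.0 mg/kg and 3.0 mg/kg"), so 6 × 2 × 5 = 60 subjects would be needed, but "only 48 subjects will be recruited". SAP 3.3 implies 48 − 3 − 1 = 44 on the biweekly regimen. SAP 4.5 gives one intensified subject where SAP 3.3 gives three, which would make it 46. Either way at most four dose levels can qualify (44/10 = 4.4; 46/10 = 4.6).

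**Landmark.** Among subjects still on treatment at a fixed visit, status fixed by then cannot depend on what follows, so the spurious gap goes. At Cycle 3 Day 1 the per-sample model gives 88 vs 88 days counted from the landmark. In the onset model a Day 43 landmark gives 148 vs 148 days and ORR 18% vs 18%.

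The share stopping before Cycle 3 is 1 − 0.5^(2/m) for a median of m cycles: 37% at m = 3, 29% at m = 4, 21% at m = 6. In the onset model this applies to the 90% who do not respond: 0.9 × 37% = 33% at 6 weeks, 0.9 × 50% = 45% at 4 weeks, 0.9 × 29% = 26% at 8 weeks.

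**The case against.** The strongest reply is that ADA observation does not stop with treatment. An early stopper who attends both follow-up visits has about 10 weeks of observation after the last dose. Patients with no post-baseline sample are set to missing, so some of the earliest dropouts never enter the negative group. With fast onset and full attendance the gap almost vanishes (94 vs 93 days). All of this stands, and it limits the size of the bias. It does not remove the bias: slow onset, missed visits or a high share able to form ADA bring it back. Patients who stop early for progression are also the likeliest to start another treatment and lose the later samples.

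It can also be said that both displays are descriptive, that no decision rule uses them, that the expansion part was not initiated, and that duration by ADA status is useful context for the AE tables by ADA status. That stands too, and it is why the planned table should stay.

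Finally, a landmark used as a replacement would drop subjects who stop for an early DLT. Protocol 2.1.2 links early liver toxicity with pre-existing ADA for another DR5 agent, so those subjects matter. This argues for adding the landmark display, not substituting it.

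**Conclusion.** The concern holds as a tendency of uncertain size. Duration by ADA status, and ORR by ADA positivity where the size condition is met, are open to immortal-time bias that favours the ADA-positive group. With no true ADA effect, the ratio of mean durations runs from about 1.0 (half able to form ADA, median onset two weeks, all follow-up attended) to about 3.4 in the per-sample model. It reaches 3.7 in the extreme case where every patient can form ADA and none attends follow-up. These figures rest on assumed incidence, onset, attendance and durations.

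A reader might infer more than the documents support:

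- **That only patients who stay on treatment can become ADA-positive.** The 30- and 70-day samples contradict this.
- **That ADA-positive patients are certain to look two to three times longer-treated.** The ratio can be close to 1.0.
- **That the SAP 17.2 table is meant to show whether immunogenicity shortens treatment, or that a harmful effect would be masked or reversed.** The SAP states no such purpose, and only the no-effect case was simulated.
- **That a biased ORR forest plot will appear at all six dose levels.** The size condition rules that out.

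This is a cheap improvement to secondary descriptive displays.

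**What to change.** 1. In SAP 17.2 and 15.4, keep the planned all-subject displays. Add a footnote that ADA status depends on the number of samples and the time under observation, so differences between groups cannot be read as an effect of ADA.
2. Add a landmark version of each. Include subjects still on treatment at Cycle 3 Day 1. Classify ADA by the SAP 18.1 rule from samples up to that visit. Count duration from that day and only responses first documented after it. Report how many subjects are excluded. The first scheduled on-treatment CT comes later in Cycle 3, so scheduled response assessments are not lost.

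The cost is SAP wording and one extra derivation. Subjects who stop before the landmark are absent from the added display: about 29% to 37% at a median of 3 to 4 cycles, and 21% to 45% over all the durations assumed. Only the Cycle 2 and Cycle 3 pre-dose samples would normally define status. Early toxicity by ADA must still be read from the all-subject tables. With about 44 × 0.67 = 29 to 44 × 0.71 = 31 subjects left, at most two or three dose levels could meet the SAP 4.4 condition, so the landmark ORR may be feasible only in total.
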